IMPACT OF HEAD OF BED ELEVATION IN SYMPTOMS OF PATIENTS WITH GASTROESOPHAGEAL REFLUX DISEASE: A RANDOMIZED SINGLE-BLIND STUDY (IBELGA)

INTERNAL MEDICINE POSTGRADUATE THESIS PROTOCOL

MENTOR: [name] RESIDENT: [name] RESIDENT: [name]

> BOGOTÁ D.C. MARCH 2ND, 2017

EXECUTIVE SUMMARY

Background: Gastroesophageal reflux disease is a very frequent clinical condition and nocturnal symptoms are a cause of quality of life impairment, poor sleep quality and absenteeism. Because of factors such as a prolonged acid exposure during sleep, nocturnal reflux has been associated to esophagitis, more extra-esophageal symptoms and other illnesses such as asthma. Head of bed elevation, as a low-cost non pharmacologic anti-reflux treatment is nowadays recommended, but its clinical impact in patients with nocturnal symptoms remains unknown due to inconsistent results and methodological limitations among different clinical trials, most of which were performed before the widespread use of proton pump inhibitors in clinical practice.

Hypothesis: Head of bed elevation is a useful treatment for patients with gastroesophageal reflux disease and nocturnal symptoms, and has a positive impact in quality of life in these patients.

Study Objective: To assess the effectiveness of head of bed elevation for treatment of patients with gastroesophageal reflux disease and nocturnal symptoms, and to determine the impact of this intervention in quality of life of these patients.

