Hamilton J, 1988 [Esophagitis]	3	3 days	15	No acid exposure time reduction nor clinical improvement	Low power Short follow-up	19
Pollmann H, 1996 [GERD]	NA	2 weeks	NA	No clinical improvement	Full text unavailable Non-structured abstract	21
Khan BA, 2012 [Nocturnal GERD]	1	1 week	20	↓ acid exposure time, clinical improvement	Non-randomized Inpatient setting	18

Table 1: Summary of HBE clinical trials in GERD published to date. NA: Unavailable; PPI: proton pump inhibitor; ↓: reduction

HYPOTHESIS

Head of bed elevation is a useful treatment for patients with GERD and nocturnal symptoms, and has a positive impact in quality of life in these patients.

STUDY OBJECTIVES

General Objective: To assess the effectiveness of HBE for treatment of patients with GERD and nocturnal symptoms, and to determine the impact of this intervention in quality of life of these patients.

Specific Objectives:

- 1. To identify, recruit and randomize participants with strict allocation concealment.
- 2. To compare symptom severity and quality of life among participants allocated to the HBE and the control group, in both the first and second period of study.
- 3. To assess therapeutic adherence and adverse event occurrence periodically by means of telephone call and photographic documentation of patient compliance with assigned intervention.

PATIENTS AND METHODS

General design: Randomized single-blind single-centre controlled clinical trial with a 2x2 cross-over design, in a sample of patients attending to the outpatient visit at the Gastroenterology, Digestive endoscopy and Liver Diseases Unit in Clínica Fundadores, Bogotá city. Participants who meet the inclusion and have no exclusion criteria will be randomized to raise the head of bed with standard 20 cm-height wooden blocks or to sleep without bed inclination during 2 periods of 6 weeks each, separated by a washout 2 week period. During the trial, every patient will receive standard pharmacological treatment with a proton pump inhibitor and/or sodium alginate, according to treating physician criteria, and the researchers in charge of statistical analysis and reporting results will be blinded for the non pharmacological intervention under study. Primary outcome is a significant symptom reduction according to RDQ validated questionnaire and secondary outcomes include quality of life impact according to SF-36 validated questionnaire, patient preference and adverse events of non pharmacological intervention.

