	Actual α	0,0481262
	Proportion p12	0,4201608
	Proportion p21	0,1176592

Table 3: Sample size calculation output with G*Power 3.1.9.2 software²⁷

Inclusion criteria:

Patients with GERD who meet with all the following characteristics:

- 1. Diagnosis of GERD based on Montreal definition (Esophageal erosions and typical symptoms such as pyrosis and/or regurgitation with a frequency ≥ 2 times per week).
- 2. Retrosternal pyrosis lasting ≥ 3 months.
- 3. Pyrosis and/or regurgitation with a frequency ≥ 3 nights per week
- **4.** GERD-associated sleep disturbance (insomnia, poor sleep quality) with a frequency ≥ 3 nights per week, and lasting ≥ 1 month.

Exclusion criteria: Patients with atypical symptoms and no erosions on endoscopy (NERD: Non-erosive Gastroesophageal Reflux Disease) will not be included. Likewise, patients with the following situations will be excluded from the trial: peptic ulcer, history of biliary surgery, lactating or pregnant women, participants under 18 years of age and nighttime shift workers (12 am to 6 am). Patients with the following conditions which affect sleep quality will also be excluded: Obstructive sleep apnea

hypopnea syndrome, chronic obstructive pulmonary disease, patients with nocturnal supplementary oxygen requirement, orthopnea, nocturia, restless legs syndrome, patients consuming more than 3 cups of coffee per day, patients planning to travel beyond 3 time zones during study, patients being treated with sleep medication (e.g. anxiolytics, antihistamines, benzodiazepines) for less than 3 months or when suspension or dose modification of this drugs is being planned during the study course.

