Cross-over: After allocation has been completed, patients in the intervention group will receive a pair of numbered wooden prisms with dimensions 20x18x18 cm along with written instructions about the correct use of the intervention. The patient must sleep with HBE during 6 weeks and both RDQ and SF-36 questionnaires will be applied again at the end of this first period while the participant is still sleeping with HBE. Afterwards, a washout 2 week period follows in which the participant sleeping with HBE will stop using it and will return the pair of wooden prisms to the researchers. After washout period has ended and both RDQ and SF-36 questionnaires have been applied again, patients allocated to the control group during the first period of the study will receive a random pair of prisms and will be instructed to use the prisms for sleeping with HBE during a second period of 6 weeks. Meanwhile, participants initially allocated to the HBE group will be followed as a control group in this second period of the study.

Blinding: Because HBE is not susceptible to double-blinding, patients allocated to the intervention group will always be aware of the group they belong to. However, the researcher in charge of statistical analysis of data and writing the results report will work with random-generated alphabetical group codes for masking the intervention in each one of the periods of the trial.

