Follow-up: After participant allocation, telephonic follow up will be made during both periods of the trial with a frequency that is dependent on the intervention group of the patient in that period. Participants in the HBE group will be called weekly for 2 weeks, and then will be called biweekly for a month, until each period of 6 weeks has ended. In contrast, patients in the control group will be called every three weeks along each period. With the purpose of verifying both HBE adherence and correct use of wooden prisms, every participant will be asked to send a photograph of the bed head legs during the follow-up telephone call. The photograph will be received by the researcher via e-mail or smartphone and will be encoded and saved in a hard disk. At the end of the first period, RDQ and SF-36 questionnaires will be applied and researchers will store the returned prisms during washout period. When washout period has ended, RDQ and SF-36 questionnaires will be applied again in order to be sure of the absence of any carry-over effect in the group initially allocated to HBE. Finally at week 14, RDQ, SF-36 and Patient Preference questionnaires will be administered to complete study ending outcome assessments.

In figure 5, a schematic representation of follow-up is shown.

[figure not shown]

Figure 5: Schematic representation of photographic and telephonic follow-up. W1-6: Weeks from 1st to 6th in each period.

Primary outcome:

1. Effectiveness: Change of ≥ 0,6 points between basal RDQ questionnaire and the same questionnaire administered after 6 weeks of HBE use.

Secondary outcomes:

- 1. Quality of life: Change of ≥ 10 percentage points between basal SF-36 questionnaire and the same questionnaire administered after 6 weeks of HBE use.
- **2. Patient preference:** Proportion of patients who preferred HBE, after finishing 14 weeks of the study.
- 3. Safety: Proportion of patients with any reported adverse event during HBE or without bed inclination.

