between periods will be transformed into a binomial variable and a McNemar marginal homogeneity test will be applied. McNemar mid-p was used if discordant pairs sum was smaller than 25²⁸. Differences with one-tail p<0,05 will be accepted as statistically significant. Exploratory subgroup analysis will search for differences stratified according to age group, sex, ethnic group, BMI, comorbidities, cups of coffee per day, pharmacological adherence, and length and severity of symptoms; among other 16 baseline variables. Subgroup interactions will be tested with Chi-square or Fisher exact test, and effect size was expressed as a univariate relative risk from a generalized linear model of binomial family. As part of internal quality control of the clinical trial, a pre-test was applied to prove the assumption of a negligible *carry-over* effect, according to expert guidelines²⁹. Analysis of variance (ANOVA) for crossover studies was used in search for significant sequence, period and treatment effects, assuming a negligible *carry-over* effect. In the modified intention to treat analysis, participants with protocol violations because of bad adherence to HBE, were included, but it was not possible to include patients who withdrew from the study because outcome information could not be gathered completely.

Methodology diagram: A schematic representation of the trial methodology is presented in figure 6.

[figure not shown]

Figure 6: Schematic representation of the trial methodology. RDQ: Reflux Disease Questionnaire; SF-36: Short Form 36 Questionnaire; HBE: Head of Bed Elevation; Standard treatment: Based on proton pump inhibitors and/or sodium alginate, according to treating physician criteria.

WORK TEAM

Work team of this clinical trial is formed by three authors. The respective roles during the design and conduction of the trial, and also the professional profiles of each researcher are described below.

Researchers:

- [name] (Principal Researcher study design, patient recruiting, telephonic follow-up, outcome assessment, statistical analysis, writing of final report)
 - General Practice Physician Universidad Nacional de Colombia
 - 3rd year Internal Medicine resident Universidad Nacional de Colombia
- [name](Researcher patient recruiting, intervention administration, clinical and telephonic follow-up, writing of final report)
 - General Practice Physician Universidad Nacional de Colombia

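### Eligibility does not address patients who already sleep with the bed head raised, and no flat-bed interval precedes the basal questionnaires, so for current users a change from basal can compare elevation with elevation

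*Combined protocol and SAP*

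**What the plan says.** The executive summary of the combined protocol and SAP states: "Head of bed elevation, as a low-cost non pharmacologic anti-reflux treatment is nowadays recommended". The problem statement repeats this, noting a low level of evidence.

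Under Inclusion criteria, criterion 3 is "Pyrosis and/or regurgitation with a frequency ≥ 3 nights per week", and criterion 4 requires reflux-related sleep disturbance on at least 3 nights a week. Neither refers to sleeping position. Under Exclusion criteria, the sentence beginning "Patients with the following conditions which affect sleep quality will also be excluded" goes on to sleep disorders, coffee, travel across time zones and recently started or changing sleep medication. Current or previous HBE is not listed.

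The primary outcome is "Change of ≥ 0,6 points between basal RDQ questionnaire and the same questionnaire administered after 6 weeks of HBE use". The quality-of-life outcome has the same form, with 10 points on SF-36.

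The only interval off HBE lies between the periods (Cross-over): "a washout 2 week period follows in which the participant sleeping with HBE will stop using it". RDQ and SF-36 are repeated at its end, and the Follow-up section gives the reason as a check on carry-over. The control condition is a flat bed (General design): "to sleep without bed inclination during 2 periods of 6 weeks each".

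**The concern.** Participants come from one gastroenterology unit. The active search telephones patients whose erosive esophagitis was found at endoscopy in 2014 to 2016. Since the plan itself calls HBE a recommended measure, some of these patients may have raised the bed before enrolment.

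Such a patient can enter with a basal RDQ taken on HBE. After six weeks on the prisms the expected change is about zero, however well HBE works. The primary and quality-of-life outcomes, both defined as change from basal, then understate the response to HBE. The plan protects the start of period 2 with two weeks off HBE, but gives the first baseline no such protection.

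**Working it through.** **The plan's own figure.** Figure 2 multiplies the two improvement rates: p12 = 0.588 × 0.714 = 0.420 and p21 = 0.412 × 0.286 = 0.118, so 53.8% of pairs are discordant. With N = 34, 34 × 0.538 ≈ 18 discordant pairs. With critical value 13 the one-sided alpha is 0.0481 and power 0.8169, as in Table 3. Letting the number of discordant pairs vary, mid-p McNemar power at N = 34 is 0.81. The stated N reproduces.

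**Inputs for the check.**
- RDQ mean 3.3, SD 1.0, range 1 to 6, threshold 0.6: Sample size section.
- One-sided level 0.05 (Statistic analysis plan): "Differences with one-tail p<0,05 will be accepted as statistically significant".
- Assumed, not in the documents: correlation 0.5 between any two RDQ scores of one patient; true HBE effect 0.6; share f of current users 10%, 20% or 30%; users' earlier elevation equivalent to the prisms; basal means enrolment.

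**Responder probabilities.** SD of a change = √(2 × 1.0² × (1 − 0.5)) = 1.0.
- Flat-bed patient on HBE: mean change 0.6, P(Z ≥ 0) = 0.50, or 0.49 after bounding scores at 1 to 6.
- Current user on HBE: mean change 0, P(Z ≥ 0.6) = 0.27. A flat-bed patient in the control period has this same chance.
- Current user in the control period, now flat: mean change −0.6, P(Z ≥ 1.2) ≈ 0.11.

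**HBE response = 0.49 × (1 − f) + 0.27 × f.**
- 10%: 0.441 + 0.027 = 0.468, about 47%.
- 20%: 0.392 + 0.054 = 0.446, about 45%.
- 30%: 0.343 + 0.081 = 0.424, about 42%.

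**McNemar power.** Simulating the bounded three-score model gives discordant cells (responds on HBE only versus in control only) of 29.0% and 6.8% for flat-bed patients, and 19.7% and 4.4% for current users. Mixing them at f = 30%: 0.7 × 29.0 + 0.3 × 19.7 = 26.2%, and 0.7 × 6.8 + 0.3 × 4.4 = 6.1%. Mid-p power at N = 34:

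| Share of users | This model | Upper bound |
|---|---|---|
| 0% | 72% | 81% |
| 10% | 70–71% | 77% |
| 20% | 69% | 72% |
| 30% | 67–68% | 66% |

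Ranges are the spread between runs of the same model. Its 72% starting value lies below the plan's 81% because it yields fewer discordant pairs (29.0 + 6.8 = 35.8% against 53.8%). That gap has nothing to do with current users.

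The upper bound keeps the Figure 2 cells and multiplies both by (1 − f), so users never respond in either condition. The HBE response is then 0.588 × (1 − f): 52.9%, 47.0% and 41.2%.

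**Period contrast.** In the same model the mean control-minus-HBE difference is 0.58 in users and non-users alike. Paired-t power on that difference at N = 34 is 96% at every share.

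**The case against.** The strongest reply is that the central quantity is missing. No section says how many candidates use HBE, and if few do, little is lost. That stands, and it is why only a range can be shown.

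Second, the hypotheses compare RDQ with and without HBE, and the analysis plan includes a crossover ANOVA. A current user lies flat in the control period and still contributes an HBE-versus-flat difference. This stands too. A reader might infer that the whole treatment comparison is contaminated, but the period contrast is not. The McNemar variable is described as built from the score difference between periods, so it is exposed only if it is formed from changes from basal.

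Third, a reader might infer that every current user's primary outcome is HBE against HBE. That depends on which RDQ is basal. Enrolment is the plain reading, because the post-washout RDQ is given a carry-over purpose. However, the timeline table (possibly broken in extraction) marks basal questionnaires well after patient sampling. If basal meant week 8 for control-first patients, their reference would follow eight weeks flat (6 + 2), and only HBE-first users would be affected.

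Fourth, the entry rules might be read as selecting patients in whom HBE has failed. The criteria show only that symptoms are not below the entry threshold. Partial response, or a lower elevation than 20 cm, fits equally well.

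Finally, the telephone format, the basic data form and most of the baseline variables are not visible, so prior HBE may be asked about or recorded. Recording it would be neither an exclusion nor a washout.

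**Conclusion.** The gap is real and worth closing. As written, a current user can enter with a basal RDQ and SF-36 taken on HBE, and the change-from-basal outcomes for that patient can then compare HBE with HBE, subject to the sequence and the meaning of basal. The bias in the HBE responder proportion is toward the null.

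Its likely size is modest: about 2 points of HBE response and 1 to 2 points of McNemar power at an assumed 10% of users, and about 7 and 4 to 5 points at 30%. These figures rest on the assumed shares, correlation and effect, and on basal meaning enrolment for everyone.

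The fall from 81% to 66% should not be taken as the expected loss. It needs users never to respond in either condition, whereas the model gives them a 27% chance on HBE, and their discordant pairs still favour HBE (about 20% against 4%). No figure stated in the plan is wrong because of this gap.

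**What to change.** Add one question on current bed-head elevation (blocks, wedge, adjustable bed) to the standardized telephone format, and one eligibility line. Either exclude current users, or admit them only if the basal RDQ and SF-36 are taken, and inclusion criteria 3 and 4 rechecked, after the same two-week flat-bed interval that the plan uses between periods. State which RDQ and SF-36 count as basal for each sequence. Record prior HBE as a baseline variable.

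If enrolment is complete, ascertain prior use and report the primary outcome without current users as a sensitivity analysis.

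The cost is a few candidates lost or delayed by two weeks, in a trial that already reports slow recruitment. The stated N of 34, raised to 42, does not change.

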Sample size was estimated based on the hypothesis that HBE would produce a difference of at least 10% in RDQ and SF-36 scores. Effect size (Cohen d) was calculated as 0,49 keeping in mind an RDQ mean and standard deviation of 3,3±1,0 previously found in Spanish population with symptomatic GERD²⁴ and an SF-36 mean and standard deviation of 56,9±20,3 reported in Italian population in medical therapy with PPI²⁵. The minimally important difference selection was chosen based on the assumption that any difference smaller than 10% would have no clinical relevance. Based on this data, 14 patients per group would yield a power greater than 80% for detection of a minimally important difference as large as or larger than 0,6 points in RDQ questionnaire (range: 1 to 6) and 10 points in SF-36 questionnaire (range: 0 to 100), when using a paired t test as described in the statistical analyses plan section. Because of a complementary analysis of crossover data is planned with McNemar marginal homogeneity test, effect size was recalculated based on results of a previous trial²⁰, according to which, 58,8 % and 28,6% of placebo-treated patients in pre-omeprazole era, reported improvement of GERD symptoms with and without a HBE of 20 cm, respectively. Based on these data, and maintaining a statistical power of 80%, required sample size was adjusted to a total of 34 patients. In

figure 2, matrices for sample size calculation are shown, based on the cited trial and using internationally accepted statistical procedures²⁶. Likewise, in table 3 an output of sample size calculation is shown from G*Power 3.1.9.2 (Universität Düsseldorf, Düseldorf, Germany) software²⁷. Finally, calculated sample size was increased by 20% in order to avoid study power loss due to drop-outs or losses of follow-up. Thus, final sample size was 42 patients, 21 per group.

T test	Means: Difference between two dependent means	(matched pairs)
Analysis	A priori: Compute required sample size	
Input	Tails	One
	Effect size dz	0,4926108
	A err prob	0,05
	Power (1- β err prob)	0,8
Output	Noncentrality parameter δ	2,5596808
	Critical t	1,7056179
	Degrees of freedom	26
	Total sample size	27
	Actual power	0,8015888
McNemar	Proportions: Inequality, two dependent groups	
Analysis	A priori: Compute required sample size	
Input	Tails	One
	Odds ratio	3,571
	α	0,05
	1- β	0,8
	Prop discordant pairs	0,53782
Output	Lower critical N	13,0000000
	Upper critical N	13,0000000
	Total sample size	34
	Actual power	0,8169370

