Figure 3: Schematic representation of HBE and expected bed inclinations.

Randomization: A list of 42 numbers will be generated, with subsequent binomial transformation, by using STATA 13.0 software for Windows (StataCorp LP, Texas, USA) in order to allocate participants in a 1:1 proportion to each one of the study arms. Wooden prisms will be marked with a consecutive number from 1 to 42 and they will be stored, keeping the marked number out of reach from the sight of the researcher in charge of patient recruiting.

Patients that meet the inclusion criteria, have no exclusion criteria and who give written informed consent, will be assigned a consecutive number during their outpatient visit according to their order of inclusion in the trial. These participants will be randomized to either HBE or control group in the moment that a member of the research team verifies, among the stored prisms, the existence of a prism pair marked with the same number as the consecutive number assigned to the patient. In the case that this pair does exist, then the patient will take home that pair of wooden prisms and use them during the first period of the trial according to spoken and written instructions to be given at that moment. On the contrary, if a pair of wooden prisms marked with the same consecutive number as the patient, does not exist, then it will be understood that the study participant has been allocated to control group during the first period of the trial. The member of the research team who verifies the storehouse of wooden prisms will not be in charge of confirming inclusion and exclusion criteria and will not assign consecutive numbers to patients during outpatient visits.

Allocation concealment: The researcher in charge of confirming inclusion and exclusion criteria, fulfilling the Basic Data Formulary and providing the patient with the Informed Consent Format, will not be aware of the allocation sequence order until these 3 documents have been applied to the participant and a consecutive number has been generated according to their order of inclusion in the trial. After that, a member of the research team in the prism storehouse will verify the existence of a prism pair marked with the same number as the consecutive number assigned to the patient, and only in that point allocation status of the participant will be known.

[figure not shown]

Figure 4: Wooden prisms quality control. ICR: Interquartile range; Q1: Quartile 1; Q3: Quartile 3.

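### The allocation rule is not defined, so 21 patients per sequence is not assured, and the complementary McNemar analysis has no period term to absorb an unequal split

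*Combined protocol and SAP*

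**What the plan says.** The Randomization section describes the list in one sentence: "A list of 42 numbers will be generated, with subsequent binomial transformation", done in STATA, "in order to allocate participants in a 1:1 proportion to each one of the study arms". It does not say how a number becomes an arm. It mentions no cut-point, block size, fixed total or stratification.

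The Sample size section reaches the target in two steps. For the McNemar comparison, "required sample size was adjusted to a total of 34 patients"; then the "calculated sample size was increased by 20% in order to avoid study power loss due to drop-outs" or losses to follow-up. It concludes: "Thus, final sample size was 42 patients, 21 per group".

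The Statistic analysis plan dichotomises the between-period score difference and applies McNemar's test as complementary processing of the RDQ and SF-36 outcomes, with the mid-p version when there are fewer than 25 discordant pairs. The threshold is one-sided: "Differences with one-tail p<0,05 will be accepted as statistically significant". A crossover ANOVA is named separately to look for sequence, period and treatment effects. The McNemar comparison has no period or sequence term.

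**The concern.** The Statistic analysis plan uses the word binomial for a variable cut into two categories. Read the same way, the Randomization section turns each of the 42 random numbers into a 0 or a 1. If that is done number by number with a fixed cut, it is simple randomisation: 1:1 on average, with no guarantee of 21 and 21.

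In a 2x2 crossover, equal sequences make a period effect cancel from a comparison that ignores period. With unequal sequences, part of it is read as an effect of head-of-bed elevation (HBE). A period effect is plausible here. Entry requires symptoms on at least 3 nights per week, so some regression to the mean is likely, and background drug treatment is left to the treating physician. The analysis at risk is the one that set the sample size at 34 before inflation.

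**Working it through.** **1. The plan's own figures.** Inputs from Sample size and Table 3: N = 34, discordant share 0.53782, one-sided α = 0.05.
- Discordant pairs: 34 × 0.53782 = 18.3, taken as 18. With critical value 13, α = 0.0481 and power = 0.8169, as in Table 3.
- Inflation: 34 × 1.2 = 40.8, so 41, and 42 when made even; 42/2 = 21. The stated total and split are reproduced.

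**2. Chance of the stated split.** Assumption A: 42 independent draws at 0.5. The size of one sequence is Binomial(42, 0.5), with SD √42/2 = 3.24.

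| Split | Probability |
|---|---|
| exactly 21/21 | C(42,21)/2^42 = 0.122 |
| 24/18 or worse | 0.441 |
| 25/17 or worse | 0.280 |
| 27/15 or worse | 0.088 |

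Assumption B: the 42 numbers are cut at their median or by rank. Then 21/21 is certain. The text does not say which applies.

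**3. Precision.** The variance ratio of the period-adjusted effect at 25/17 is (1/25 + 1/17)/(2/21) = 1.038. Averaged over all splits under A, the efficiency loss is 1/42 = 2.4%. With Table 3's dz of 0.4926, N = 42 and 40 df, one-sided power is 93.2% at 21/21, 92.4% at 25/17 and 91.3% at 27/15.

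**4. Period effect in an unadjusted mean.** Let τ be the HBE effect and π the period 2 minus period 1 effect. The expected HBE-minus-control difference is τ − π in HBE-first patients and τ + π in control-first patients. The average over all patients is τ + π(n_control-first − n_HBE-first)/N. At 25/17 the multiplier has size 8/42 = 0.19.

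The documents give no period effect. For assumed values of 0.2 and 0.5 RDQ points the shift is 0.19 × 0.2 = 0.04 and 0.19 × 0.5 = 0.10, against the plan's 0.6-point threshold.

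**5. Period effect in the McNemar test.** Assume no HBE effect, improvement rates of 30% in period 1 and 50% in period 2, and independence within a patient. A patient improves only in period 1 with probability 0.3 × 0.5 = 0.15, and only in period 2 with probability 0.5 × 0.7 = 0.35. Summing over all tables, with mid-p below 25 discordant pairs and the asymptotic test otherwise, the one-sided error rate is:
- 21/21: 4.2%
- 17 HBE-first, 25 control-first: 8.6%
- 25 HBE-first, 17 control-first: 1.9%

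A test that compares sequences among discordant patients is not disturbed. In both sequences the share improving only in period 2 is 0.35/0.50 = 0.70.

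**6. What a restricted list secures.** A random permutation of 21 + 21 codes gives 21/21 if all 42 enrol. So do blocks of 2, 6 or 14, which divide 42, or mixed blocks that sum to 42 (for example three of 4 and five of 6: 12 + 30). Blocks of 4 alone do not: ten full blocks leave 2 places, and 21/21 then has probability 4/6 = 67%.

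**The case against.** The strongest reply is that the premise is not in the text. A reader might infer that the binomial transformation cannot deliver 21 per group, or that the trial's sequences are unequal. The documents support neither. The transformation is undefined, a median or rank split of a prepared list of 42 fits the wording, and no achieved split is given. This part of the reply stands: the finding is that balance is not assured, not that it fails.

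It is also true that independent 50:50 draws satisfy a 1:1 ratio in expectation, so the tension is with "final sample size was 42 patients, 21 per group" and not with the ratio. Simple randomisation is valid. Over repeated randomisations the imbalance has mean zero, so the shifts in steps 4 and 5 are conditional on a given split and can go in either direction. The average absolute imbalance under A is 12% of N, smaller than the 19% used for illustration.

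A reader might further infer that the whole primary analysis is exposed. It is not. The crossover ANOVA examines period. A paired t test appears only in the Sample size section, while the Statistic analysis plan names unpaired tests. McNemar is described as complementary.

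Finally, a fixed total is not free. Patients and the team member at the prism store know the allocation, so the last assignments become easier to guess, although the numbered store limits this. Withdrawals, which the modified intention-to-treat analysis leaves out, can also undo the balance.

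What remains is an unspecified rule, an unsecured target of 21 per group, and a binary analysis of the primary outcome and quality of life with no allowance for period.

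**Conclusion.** The point holds as a minor one. Under independent draws the stated split would occur about once in eight lists, and 25/17 or worse in 28% of them; under a median or rank split the problem would not arise. Loss of power is not the issue: less than one percentage point at 25/17 in the check above.

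The consequence is limited to comparisons that ignore period, chiefly McNemar. At 25/17 these take in 0.19 of a period effect on the mean scale. In the one illustrative binary scenario, the one-sided error moves from about 4% to about 9% or about 2%, depending on which sequence is larger. Those sizes rest on assumed period effects (0.2 to 0.5 RDQ points; 30% against 50% improving) and on within-patient independence, none of which the documents supply.

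**What to change.** - **State the rule.** Give the exact STATA step that turns the 42 numbers into arms, with the seed.
- **Fix the total.** Generate the list as a random permutation of 21 HBE-first and 21 control-first codes, or as concealed blocks of varying size that sum to 42. Keep the prism-numbering concealment unchanged. The cost is one line of code and slightly more predictable late allocations.
- **Report the split.** Give the numbers randomised and analysed in each sequence. This matters in any case, since drop-outs can undo the balance and parts of the protocol, written in the past tense, suggest that the list may already exist.
- **Adjust the binary comparison for period.** Alongside the crossover ANOVA, add a period-adjusted version of the McNemar analysis, for example the Mainland-Gart test: among discordant patients, cross-tabulate sequence against the period in which the patient improved and apply Fisher's exact test. It needs no new data. Its power is not covered by the plan's calculation of 34 patients and should be checked before it replaces McNemar.
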